7.2.5.3. Clinical outcome assessments

Endpoints for secondary objectives regarding joint health, quality of life, and pain will be based on validated standardized measurements. Specifically, joint health will be assessed over time based on the Hemophilia Joint Health Score (HJHS), quality of life will be

Proprietary and Confidential

assessed based on the Haemo-Quality of Life assessment (QoL-A) questionnaire, and pain will be assessed based on the Brief Pain Inventory-Short Form (BPI-SF). These measured are described in Sections 7.2.5.4, 7.2.5.5, and 7.2.5.6, respectively. Analyses of these instruments are described further in Section 10.3 and the SAP. As these instruments standardize collection of data for areas that are monitored in routine clinical practice, the assessments are expected to follow routine clinical follow-up. Physicians participating in the AbD are expected to enter data for these instruments collected relative to the study index date per the data elements of interest (Table 2).

7.2.5.4. Hemophilia Joint Health Score

The HJHS is a validated outcome tool developed for the assessment of joint health in people with hemophilia (Feldman 2011). The ordinal joint score assesses 9 items in 6 index joints. The HJHS measures joint health, in the domain of body structure and function (ie, impairment), of the joints most commonly affected by bleeding in hemophilia: the knees, ankles, and elbows. This physical examination assessment tool conducted by a healthcare provider is sensitive enough to pick up the subtle early signs of joint damage. It is appropriate for monitoring joint change over time or assessing efficacy of treatment regimens in children receiving both prophylactic and on-demand therapy.

7.2.5.5. Haemo-QoL-A Questionnaire

The Haemo-QoL-A questionnaire is a validated hemophilia-specific health-related quality of life questionnaire for adults (Rentz 2008), including for adults undergoing gene therapy (Quinn 2022). It consists of 41 questions covering 6 domains (Physical Functioning, Role Functioning, Worry, Consequences of Bleeding, Emotional Impact and Treatment Concerns). Items are answered by participants on a 6-point Likert-type scale, ranging from 0 (None of the time) to 5 (All of the time). Higher scores mean better health-related quality of life or less impairment for a particular subscale. The Haemo-QoL-A has a recall period of the “past 4 weeks” (Quinn 2022).

7.2.5.6. Brief Pain Inventory-Short form Questionnaire

The BPI-SF is a validated and frequently used patient-reported questionnaire that assesses pain severity and the impact of pain on daily functions (ie, pain interference) (Cleland 2009). The BPI-SF measures generic pain (ie, is not indication-specific) has been used and validated in hemophilia (Kempton 2017; Srivastava 2020; Chantrain 2023).

Four questions measure pain intensity (worst pain, least pain, average pain, and pain now). The pain intensity items use an 11-point numerical scale with zero signifying ("no pain") and 10 signifying ("pain as bad as you can imagine"). The pain interference scale assesses the degree to which pain interferes with 7 constructs (General activity, Mood, Walking ability, Normal work, Relation with people, Sleep, and Enjoyment of life). The pain interference items use an 11-point numerical scale with zero signifying "does not interfere" and 10 signifying "completely interferes." Both the pain intensity and pain interference items have a

recall period of the “last/past 24 hours”. Four other items allow participants to report on the nature of their pain.

7.2.5.7. Safety outcomes

Safety events of interest (all cause death, hemophilia-related death, adverse events leading to hospitalization and/or death, and targeted adverse events of development of FVIII inhibitors, thromboembolic events, new malignant neoplasms, and severe liver disease) will be described for each cohort based on data recorded in the DHR. See [Table 8](#) for detail on events captured and relevant data field when applicable. Safety events will be described and compared based on events recorded starting on the index date and throughout the follow-up period for each participant.

Refer to [Section 9](#) for additional information on safety reporting expectations.

Table 8: Safety Events of Interest

Variable	Description	Captured in DHR	Time period for Analysis	Entry into DHR	Operational notes including Relevant Data Fields in DHR
All cause death	Deaths occurring due to any cause	✓	Follow-up (inclusive of index)	Ongoing	Derived based information entered into the DHR when a participant is no longer enrolled in the DHR due to the reason being death and cause of death identified as hemophilia-related, non-hemophilia-related, or unknown. (See limitations of interpretation of events regardless of relationship to hemophilia treatment in Section 10.5).
Hemophilia-related death	Deaths occurring due to the disease	✓	Follow-up (inclusive of index)	Ongoing	Derived based information entered into the DHR when a participant is no longer enrolled in the DHR due to the reason being death and cause of death identified as hemophilia-related.
Adverse events leading to hospitalization and/or death	Medical event leading to hospitalization and/or death	✓	Follow-up (inclusive of index)	Ongoing	
The DHR captures information on medically relevant events including allergic reactions, thromboembolic events, thrombotic microangiopathy, malignant neoplasm, autoimmune disease, sensory paresthesia, infusion/hypersensitivity reaction, complications of immunosuppression and other with a free text field to specify the other category. For each event, the connection to hemophilia treatment (yes/no/unknown) is also recorded, along with serious consequences due to the event (hospitalization, death, none or unknown).
 
Event recorded as leading to hospitalization and/or death will be analyzed both for any reason (regardless of relation to hemophilia treatment) and related to hemophilia treatment. (See limitations of interpretation of events regardless of relationship to hemophilia treatment in Section 10.5).
 
Hospitalizations are defined as a participant having been admitted to the hospital for inpatient care, either to the inpatient ward or to the emergency room for observation and/or treatment that would not have been appropriate in the physician’s office or outpatient setting.

Variable	Description	Captured in DHR	Time period for Analysis	Entry into DHR	Operational notes including Relevant Data Fields in DHR
Targeted Adverse Events					
Development of FVIII inhibitors	Positive inhibitor tests and/or a positive test and the requirement for ITT	✓	Follow-up (inclusive of index)	Ongoing	Based on recording of the DHR variables for positive inhibitor tests after enrollment in the DHR, or use of immune tolerant therapy (ITT). See Table 4 and SAP for additional information on definition for positive inhibitors based on 2 positive tests or 1 test and use of ITT.
Thromboembolic events	Occurrence of a thromboembolic event related to treatment	✓	Follow-up (inclusive of index)	Ongoing	Derived based recording of medically relevant event of thromboembolic event in the DHR that has been identified as connected to hemophilia treatment. Occurrence of thromboembolic events regardless of relationship to treatment will also be described, but not compared. (See limitations of interpretation of events regardless of relationship to hemophilia treatment in Section 10.5)
Malignant neoplasms	Occurrence of a malignancy	✓	Follow-up (inclusive of index)	Ongoing	Derived based recording of medically relevant event of malignant neoplasm in the DHR. Malignant neoplasms have cells that grow uncontrollably and spread locally and/or to distant sites. Malignant tumors are cancerous (ie, they invade other sites). They spread to distant sites via the bloodstream or the lymphatic system. This spread is called metastasis. Metastasis can occur anywhere in the body (Patel 2020). Malignancies are expected to be defined consistent with other data collection occurring in the study population, including the International World Federation of Hemophilia Gene Therapy Registry (WFH 2024 ; Konkle 2020).
Severe liver disease (liver failure, liver fibrosis and/or progression of liver)	Occurrence of new severe liver disease	✓	Follow-up (inclusive of index)	Ongoing	Derived based on recording of liver disease status (liver fibrosis (new diagnosis), liver failure, and liver cirrhosis). Occurrence of severe liver disease (liver failure, liver fibrosis and/or progression of liver fibrosis, or cirrhosis). Recording during follow-up of ‘liver fibrosis (new diagnosis)’ or ‘liver failure’ will be used to identify events. Progression of fibrosis or cirrhosis will be identified based on recording of an increased Child-Turcotte-Pugh classification (eg, A → B, B→C) of liver disease relative to liver disease status at baseline or the new diagnosis of cirrhosis (Lee 2022 ; Lee 2022a ; Tholey 2023). Definitions of acute liver failure

Variable	Description	Captured in DHR	Time period for Analysis	Entry into DHR	Operational notes including Relevant Data Fields in DHR
fibrosis, or cirrhosis)					
(Tholey 2023), liver fibrosis and/or progression of liver fibrosis (Lee 2022a), or cirrhosis (Lee 2022) will be consistent with MSD Manuals for classification.
 
Similar to the description of thromboembolic events, both events regardless of relationship to hemophilia treatment and specifically related to hemophilia treatment will be analyzed. (See limitations of interpretation of events regardless of relationship to hemophilia treatment in Section 10.5).
 
The definition of severe liver disease (acute liver failure, worsening of liver fibrosis, liver cirrhosis) is consistent with other data collection occurring in the study population, including the International World Federation of Hemophilia Gene Therapy Registry (WFH 2024; Konkle 2020).

DHR, German Hemophilia Register; FVIII, Coagulation factor VIII; ITT, Immune tolerant therapy; SAP, Statistical Analysis Plan.

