4. STUDY OBJECTIVES AND ENDPOINTS

The aim of this non-interventional study is to evaluate the overall effectiveness and safety of Roctavian compared to SoC hemostatic prophylaxis treatments for PwSHA.

The specific objectives are listed below. All objectives will compare Roctavian and SoC with exogenous FVIII or emicizumab, unless otherwise noted.

Table 1: Objectives and Endpoints

[figure not shown]
Objectives	Endpoints
Primary	
To compare the annualized bleeding rate for treated bleeds.	
 Bleeding events requiring treatment with exogenous FVIII
Secondary	
To compare the annualized bleeding rate for major, life threatening, and joint bleeds.	
 Major bleeding events Life-threatening bleeding events Bleeding events occurring in the joint
To compare the proportion of people with zero bleeds for treated, major, life threatening, and joint bleeds.	
 Bleeding events requiring treatment with exogenous FVIII Major bleeding events Life-threatening bleeding events Bleeding events occurring in the joint
To compare the use of hemostatic medications.	
 Prophylactic hemostatic treatments On-demand hemostatic treatments
To compare joint health, quality of life, and pain.	
 Hemophilia Quality of Life assessment (Haemo-QoL-A) Hemophilia Joint Health Score (HJHS) Brief Pain Inventory-Short Form (BPI-SF)
To compare safety events of interest.	
 All cause death Hemophilia-related death Adverse events leading to hospitalization or death Targeted adverse events of development of FVIII inhibitors, thromboembolic events, new malignant neoplasms, and severe liver disease (liver failure or cirrhosis)
To describe time to resumption of prophylactic treatment among persons administered Roctavian.	
 Resumption of prophylactic hemostatic treatments

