5.2.2. Exclusion Criteria

Individuals are excluded from the study if any of the following criteria apply:

- Is currently in, or previously participated (in the last 12 months before index), an interventional clinical trial involving an investigational product to treat HA
- History of inhibitors against FVIII ever (or current) as recorded in the DHR prior to index
- Presence of acute infections (such as acute respiratory infections or acute hepatitis) or uncontrolled chronic infections (such as chronic active hepatitis B), and/or known significant hepatic fibrosis or cirrhosis at index

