Death			X ^g	At participant discontinuation ^g
Hemophilia-related death			X ^g	At participant discontinuation ^g
Adverse events leading to hospitalization ^h or death			X ^g	At end of study period or participant discontinuation ^g
Thromboembolic events			X ^g	At end of study period or participant discontinuation ^g
Severe liver disease (liver failure, liver fibrosis and/or progression of liver fibrosis or cirrhosis)			X ^g	At end of study period or participant discontinuation ^g
New malignant neoplasms			X ^g	At end of study period or participant discontinuation ^g

AAV, Adeno-associated virus; BPI-SF, Brief Pain Inventory-Short Form; FVIII, factor VIII; HJHS, Hemophilia Joint Health Score, QoL-A, quality of life assessment; SoC, standard of care.

a Based on data recorded in the DHR for the 12 months prior to index (or portion thereof)

b Recorded for the Roctavian Cohort only

c Assessment requested to be completed for all AbD participants on index or the 60 days prior to index and entered into the DHR consistent with routine clinical management of a participant.

d Assessment requested to be completed for all AbD participants entered into the DHR approximately every 6 months relative to the index date during follow-up consistent with routine clinical management of a participant.

e Assessment requested to be completed for all AbD participants entered into the DHR at least every year relative to the index date during follow-up consistent with routine clinical management of a participant.

f Assessment requested to be completed for all AbD participants entered into the DHR at end of follow-up (approximately 3 years after the index date) consistent with routine clinical management of a participant or at the time of discontinuation.

g Data requested to be entered through the study period including at the end of the study period (approximately 3 years after the index date) or at time of participant discontinuation.

h Hospitalization defined as a participant having been admitted to the hospital for inpatient care, either to the inpatient ward or to the emergency room for observation and/or treatment that would not have been appropriate in the physician’s office or outpatient setting.

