Hepatitis C Virus (HCV) status	History of HCV, along with treatment of infection	✓	Any time prior to index	Ongoing	Description of cohorts. Based on HCV status recorded in the DHR, including but not limited to: History of HCV (cured infection vs no infection history) Treatment for HCV eradication during baseline Presence of acute or uncontrolled chronic hepatic infections at index is an exclusion criteria. HCV status as documented in the DHR will be used to describe the population, as well as confirm inclusion/ exclusion criteria. Exclusion criteria will additionally confirmed at time of enrollment based on DHR field confirming that the participant fulfills the AbD inclusion/exclusion criteria.
Chronic liver disease status	Presence of liver fibrosis and/or cirrhosis	✓	Baseline	Ongoing	Description of cohorts. Based on liver disease (eg, report of fibrosis) recorded in the DHR. Presence of known significant hepatic fibrosis or cirrhosis at index is an exclusion criteria, which will be confirmed at time of

Variable	Description	Captured in DHR	Time period for Analysis	Entry into DHR	Operational notes including Relevant Data Fields in DHR
					enrollment based on DHR field confirming that the participant fulfills the AbD inclusion/exclusion criteria. Definitions of acute liver failure (Tholey 2023), liver fibrosis and/or progression of liver fibrosis (Lee 2022a), or cirrhosis (Lee 2022) will be consistent with MSD Manuals for classification. Fibrosis status as documented in the DHR will be used to describe the population.

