Baseline/prior pain (eg, BPI-sf)	X	X	✓	To be considered depending on statistical association and correlation with other variables (eg, target joints and HJHS)
Baseline/prior QoL (eg, Haemo-QoL-A)	X	X	✓	To be considered depending on statistical association and correlation with other variables
Activity status	X	X	✓	Not considered as this there is no validated questionnaire for lifestyle factors in PwSHA
Baseline/prior history of liver fibrosis/cirrhosis	✓	X	X	Significant liver fibrosis/cirrhosis is accounted for by the exclusion criteria, but less severe liver fibrosis to be considered based on statistical association
Baseline/prior history of hepatitis B and C	✓	X	X	Not considered as this is accounted for by study exclusion criteria
Baseline/prior history of HIV positivity	✓	X	X	Include based on statistical association
Baseline/prior history of cancer	✓	X	X	Include based on statistical association
Baseline/prior history of hypertension	✓	X	X	Include based on statistical association
Baseline/prior history of osteoporosis	✓	X	X	Include based on statistical association
Adherence to treatment	✓	X	X	Not considered as there is not enough prior literature/evidence to suggest as factor related to bleeding outcomes; confirmed by clinical expert
Genotype	X	X	X	Not considered as this is a factor for inhibitor development but not bleeding outcomes and accounted for by study exclusion criteria for history of or current inhibitors

ABR, Annualized bleeding rate; BMI, body mass index; EHL, extended half-life; FVIII, coagulation factor VIII; HIV, human immunodeficiency virus; HTC, hemophilia treatment center; PD, plasma-derived; PwSHA, people with severe hemophilia A; QoL, quality of life; SHL, standard half-life.

Note: Other variables identified in the literature review but not outlined in [Table 9](#), due to lack of relevance to this study and the association comparing Roctavian and SoC and bleeding outcomes, were ethnicity, treatment duration, pharmacokinetic (PK)-guided dosing use, prophylaxis vs on-demand treatment, concurrent medications (bypass agents, non-steroid anti-inflammatory drugs, tranexamic acid, and corticosteroid), and hemophilia severity.

Proprietary and Confidential

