 - In addition to variables that are not feasible to capture in an observational registry, the non-interventional nature of the study reflecting a range of real-world practice in Germany could introduce confounding that cannot be fully addressed with PS or specific applications of the PS (e.g. matching). For example, PwSHA are recommended to be treated with hemostatic prophylaxis, though a small portion of the severe hemophilia A population in Germany may still be utilizing an on-demand treatment regimen. Persons utilizing an on-demand regimen are likely to have a higher baseline bleeding rate, as prophylaxis is associated with reduced bleeding events. All persons administered commercially available Roctavian are expected to have received hemostatic prophylaxis treatment for at least 12 months by the time that a participant will be treated with Roctavian gene therapy. If persons treated with an on-demand regimen for part of the baseline period enroll into the SOC Cohort, these participants may have outlier propensity scores which may not be able to be matched. The proportion of on-demand participants in the SOC Cohort, as well as impact of these participants on the analysis will be discussed in interim and final reports.
- **Loss to follow-up:** Participant retention through the end of the expected observation period will be monitored carefully and attempts will be made to obtain follow-up data from participants who discontinue treatment. However, some participants may have fewer than three years of follow-up data available. Participants in the SoC Cohort are expected to have follow-up twice per year whereas participants in the Roctavian Cohort may have more frequent touchpoints due to them being on a newer treatment.
- **Missing data:** The data leveraged for this study are dependent on physicians and hospitals to accurately record each event. Methods are in place for handling missing data (Section 9.7.5) and a sensitivity analysis of missing data will be conducted.
- **Heterogeneity of SoC:** The assumption of treatment consistency specifies that there is no ambiguity defining a treatment. This assumption is also known by the term "treatment variation irrelevance". For this study, the two compared treatment groups are Roctavian versus SoC with SoC being different for various participants. Therefore, treatment consistency is approximately

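### The compared outcome severe liver disease has no single definition, and its progression rule cannot register fibrosis that worsens short of cirrhosis

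*Protocol*

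**What the plan says.** **Name of the outcome.** Table 1 in protocol Section 4 lists "severe liver disease (liver failure or cirrhosis" among the targeted adverse events. The protocol synopsis, the SAP abstract and SAP Table 1 say the same. Table 2 in protocol Section 7.1 has "Severe liver disease (liver failure, liver fibrosis and/or progression of liver fibrosis or cirrhosis", and Table 8 in Section 7.2.5.7 has "Occurrence of severe liver disease (liver failure, liver fibrosis and/or progression of liver fibrosis, or cirrhosis". Later in the same Table 8 cell the definition is restated as acute liver failure, fibrosis that worsens, and cirrhosis. That version does not mention newly diagnosed fibrosis.

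**Rule for counting.** Table 8 takes a register entry of new fibrosis or of liver failure during follow-up as an event. It then says: "Progression of fibrosis or cirrhosis will be identified based on recording of an increased Child-Turcotte-Pugh classification", relative to baseline, with newly diagnosed cirrhosis as the alternative route. SAP Table 5 repeats this rule and adds another, a higher grade of fibrosis or cirrhosis than at baseline.

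**Who can be in the study.** Protocol Section 5.2.2 excludes "known significant hepatic fibrosis or cirrhosis at index". Table 9 in Section 10.3.3.1 accepts that less severe fibrosis may be present at baseline.

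**Use.** Protocol Section 10.3.7.5 compares safety outcomes between cohorts, as relative risks under the treatment policy estimand and incidence rate ratios under the hypothetical estimand.

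**Hepatitis C.** Table 9 and SAP Table 6 drop hepatitis B and C history from the propensity score candidates: "Not considered as this is accounted for by study exclusion criteria". Table 4 in Section 7.2.3 plans to describe "History of HCV (cured infection vs no infection history".

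**The concern.** A compared safety outcome needs one definition, and a counting rule that the data source can feed. Here the name in the objectives and the rule in Table 8 select different events, and the rule does not follow a severity order. At stake is what the liver comparison can conclude for a product that, by protocol Section 3.2.2.1, acts in liver cells. The SAP shells in Annex 12.1 (Tables 15 and 16) split severe liver disease by relatedness to treatment but not by component. A reader of the report could not tell whether a difference between cohorts reflects failure or cirrhosis, or newly noted fibrosis of any degree.

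The hepatitis C entry is a smaller, separate matter: a collected liver risk factor is set aside for a reason that the eligibility criteria do not bear out.

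**Working it through.** No arithmetic applies, because the documents give no rate for fibrosis, cirrhosis or liver failure. The check traces each change in liver status through the definitions.

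**Register categories.** SAP Table 3 (Section 7.4.1) lists the liver status values: not specified, fibrosis as a new diagnosis, chronic fibrosis, cirrhosis Child A, B or C, and liver failure. Child class belongs to cirrhosis only. Fibrosis is either new or chronic and has no grade.

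| Change after index | Objectives | Table 8 counting rule | Table 8 restated definition |
|---|---|---|---|
| No fibrosis to new fibrosis, any degree | no | **yes** | not listed |
| Known milder fibrosis to worse fibrosis, no cirrhosis | no | no | **yes** |
| Any state to new cirrhosis | yes | yes | yes |
| Liver failure | yes | yes | yes (acute) |
| Cirrhosis at baseline, Child class rises | not addressed | yes | not addressed |

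**Row 1.** The counting rule sets no stage threshold, so mild fibrosis noted for the first time enters an outcome labelled severe.

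**Row 2.** This participant has no new fibrosis diagnosis, no Child class and no new cirrhosis, so no branch of the rule applies. Yet both the opening wording and the restated definition in Table 8 list worsening fibrosis. The higher-grade rule in SAP Table 5 would count it, but the listed categories provide no fibrosis grade.

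**Row 5.** A rise from baseline needs a baseline class, and known cirrhosis is excluded. Someone with unrecognised cirrhosis at index also has no recorded class, so his first cirrhosis record counts as new cirrhosis. This route has essentially no eligible participants.

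**Hepatitis C.** Section 5.2.2 excludes acute and uncontrolled chronic infection. Cured infection is neither, so a man with cured hepatitis C is eligible, and Table 4 expects such men in the cohorts. The exclusion criteria therefore do not account for that history. Sections 7.1.1 and 10.3.3 also say that the Table 4 characteristics inform the propensity score.

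**The case against.** Several points on the other side stand.

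- **Fibrosis that becomes cirrhosis is counted.** Newly diagnosed cirrhosis is an explicit route in Table 8. Only worsening short of cirrhosis is missed. The unused Child-class branch adds no bias by itself.
- **Narrowing is not the only repair.** Table 8 says its definition agrees with an international gene therapy registry, and a broader outcome may be preferred for a liver-directed product. The objectives could be widened instead. A narrower outcome would still not capture worsening fibrosis.
- **Register fields may change.** Protocol Section 7.2.2 allows fields to be added or modified, so the gap is established for the categories now listed, not for all time.
- **Hepatitis C is not lost.** Protocol Section 10.3.4.1 checks balance on characteristics outside the score as well. The SAP baseline shell (Annex 12.1, Table 3) shows hepatitis C infection before and after weighting. SAP Section 7.9.4.5 lets covariates that remain imbalanced enter the safety models.

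A reader might infer that closer follow-up of the Roctavian cohort will drive the composite, since SAP Section 7.10 says "participants in the Roctavian Cohort may have more frequent touchpoints due to them being on a newer treatment". The documents do not support that. The sentence is about loss to follow-up and contact frequency, not liver assessment, and no fibrosis rate is given. Differential detection is possible but unquantified. Secondary p-values are in any case nominal (SAP Section 7.9), and protocol Section 10.5 already warns of spurious safety findings.

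**Conclusion.** The inconsistency is certain from the text. The three wordings disagree on two of the five changes traced, new fibrosis and worsening of known fibrosis, and the counting rule treats those two in the reverse of what a severity label implies. The Child-class route is empty for eligible participants, and the higher-grade rule cannot be applied to fibrosis. This rests on the register categories in SAP Table 3 being complete.

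The finding concerns definition and reporting of a secondary safety outcome; the primary analysis is untouched. It does not show that the comparison is biased, or in which direction. The stated reason for dropping hepatitis C history is wrong for cured infection. Given the balance checks and the option to adjust, that is a minor correction and not evidence of an unadjusted comparison.

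**What to change.** Before the first data cut, which is also when protocol Section 10.3 requires the SAP to be final:

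1. Reconcile the objectives in both documents, protocol Tables 2 and 8 and SAP Table 5 to one definition of severe liver disease that the register field can support. Whether it includes new fibrosis is the sponsor's choice, but the objectives and the counting rule must agree.
2. Whichever definition is kept, report liver failure, new cirrhosis and new fibrosis diagnosis in separate rows beside any composite in SAP shell Tables 15 and 16.
3. Remove Child-Turcotte-Pugh class and the higher-grade rule as measures of fibrosis progression, or state plainly that worsening fibrosis short of cirrhosis is not captured.
4. In protocol Table 9 and SAP Table 6, replace the stated reason for hepatitis C and list its history (cured versus none) as a candidate covariate.

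The cost is wording and a few table rows; no new data are needed. If the narrower definition is chosen, the composite will hold fewer events, but the separate rows keep new fibrosis visible.
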